9.1.1 Study Activities

Table 1 Study Activities (Day 1/Baseline Through 6 months)

	Data Collection/Observation	Baseline ^a	Week 12 (V2) ± 7 days	Week 24 (V3) ± 7 days	Early Termination / Drop out	70 days after the Week 24 or the last dose	150 days after the Week 24 or the last dose
Clinician Packet	Inclusion/exclusion form	X					
	Clinical history/patient demographics	X					
	Comorbidities	X					
	DAS28 (ESR) or DAS28 (CRP)	X	X	X	X		
Patient Packet	EuroQoL 5-Dimension (EQ-5D)	X	X	X	X		
	Short Form 36-Item Health Survey (SF-36)	X	X	X	X		
	Health Assessment Questionnaire (HAQ)	X	X	X	X		
	Work Productivity and Activity Impairment Questionnaire (WPAI)	X	X	X	X		
	Healthcare Resource Utilization (HCRU)	X	X	X	X		
	Patient Global Impression of Change (PGIC)		X	X	X		
	Patient Treatment Satisfaction Questions	X	X	X	X		
Clinical n	Adverse events (including malignancy)	←				→	
	Pregnancy	←					→

a. The Baseline visit date will serve as the reference for all subsequent visits. A \pm 7 day window is permitted around scheduled study visits.

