9.5 Study Size

Approximately 52 patients diagnosed with RA will be recruited. The planned sample size provides 80% power for detecting a statistically significant improvement in HAQ-DI (Δ HAQ-DI < 0) assuming a mean Δ HAQ-DI of -0.21 and a standard deviation of 0.5 (reference 11), at two-sided significance level of 0.05 and accounting for a 10% dropout rate. The sample size also provides 99% power for detecting a statistically significant clinically meaningful improvement in HAQ-DI (Δ HAQ-DI < -0.22) assuming a mean Δ HAQ-DI of -0.5 and a standard deviation of 0.7, at two-sided significance level of 0.05 and accounting for a 10% dropout rate.

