9.7.4 Primary Endpoint Analysis

The primary endpoint variable will be the change in HAQ DI score at week 24 after the initiation of adalimumab, in those patients continuing on adalimumab.

The objective of the primary endpoint analysis will be to demonstrate that treatment with adalimumab improves functioning as measured by the HAQ DI in subjects with RA following treatment initiation. This change will be summarized as the mean and 95% confidence interval and will be tested with a paired t-test.

The primary analysis will be summarized as the mean and 95% confidence interval and will be tested with a paired t-test without adjusting for baseline disease severity. For sensitivity analysis, the mean change in HAQ DI at week 24 will be analyzed using ANOVA adjusting for baseline disease severity.

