### 2.1 Primary Objectives

- To describe the change in HAQ DI score at 24 weeks after the initiation of adalimumab (i.e. baseline), in those patients continuing on adalimumab (as observed population). This change will be summarized as the mean and 95% confidence interval or median (Q1,Q3) and will be tested with

a paired t-test or paired Wilcoxon signed-rank test without adjusting for baseline disease severity. For sensitivity analysis, the mean change in HAQ DI at Week 24 will be analyzed using ANCOVA adjusting for baseline disease severity.

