### 5.3 Analysis Plan for Primary Objectives

The objective of the primary endpoint analysis will be to demonstrate that treatment with adalimumab improves functioning as measured by the HAQ DI score in subjects with RA following treatment initiation (i.e. baseline).

- The changes in HAQ DI score at 12 and 24 weeks after the initiation of adalimumab will be presented (Excel Table 3.1); these changes will be summarized as the mean, SD, minimum, maximum, median, Q1, Q3; as well as the number and percent of patients achieving a clinically meaningful improvement on the HAQ DI, as defined by a -0.22 point improvement or greater. In addition, the mean or median change will be tested with a paired t-test or paired Wilcoxon signed-rank test without adjusting for baseline disease severity; for sensitivity analysis, the mean change will be analyzed using ANCOVA adjusting for baseline disease severity.
- The change in HAQ DI score at 24 weeks after the initiation of adalimumab (mean, SD, minimum, maximum, median, Q1, Q3), in those patients continuing on adalimumab (observed population) will be compared with those patients not continuing on adalimumab (withdrawal population). The mean or median changes in these two groups will be compared using an independent t-test or paired Wilcoxon signed-rank test listed in the table (Excel Table 3.2).

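### In a single arm, the ANCOVA labelled as the sensitivity analysis returns the raw mean HAQ DI change in the same patients, and its usual standard error is too small for the population mean when baseline DAS28 predicts change

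*SAP*

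**What the plan says.** The study follows one cohort starting adalimumab and has no control arm (Protocol 9.1, SAP 3.1). The primary endpoint is the change in HAQ DI at week 24 in patients continuing on adalimumab. It is tested by a paired t-test or, in the SAP, a Wilcoxon signed-rank test, in both cases unadjusted.

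One analysis is labelled a sensitivity analysis for this endpoint. SAP 2.1 puts it as "For sensitivity analysis, the mean change in HAQ DI at Week 24 will be analyzed using ANCOVA adjusting for baseline disease severity", and SAP 5.3 as "for sensitivity analysis, the mean change will be analyzed using ANCOVA adjusting for baseline disease severity". SAP 2.2 repeats it for week 12. Protocol 9.7.4 has the same idea with a different model: "the mean change in HAQ DI at week 24 will be analyzed using ANOVA adjusting for baseline disease severity". The SAP document history (V0.3) explains the switch to ANCOVA by the use of DAS28 as a continuous variable.

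Neither document names a group factor, the DAS28 value at which the adjusted mean is taken, whether DAS28 is centred, which coefficient is tested, or how its standard error is obtained.

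SAP 3.5.5 doubts that missing data are missing at random and applies no imputation beyond questionnaire items and incomplete dates. SAP 5.3 also plans a comparison of continuing with withdrawn patients (Excel Table 3.2). Protocol Table 1 schedules the HAQ at baseline, week 12, week 24 and "Early Termination / Drop out".

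**The concern.** A sensitivity analysis should change something that the primary analysis relies on and show whether the conclusion survives. Covariate adjustment does this in a comparative trial, where it deals with imbalance between groups. Here there is no second group to be imbalanced against, and the patients and the handling of missing data are the same as in the primary analysis.

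The stake is interpretation. A report could say that the improvement held in a sensitivity analysis when agreement was guaranteed by algebra. If DAS28 predicts change, that analysis would also show a narrower interval than the paired t-test. Meanwhile the main weakness of the estimate, its restriction to patients who stay on treatment and have data, would go unexamined. That weakness is not remote: SAP 1.1 puts average use of the drug for RA in China at 3 months, while the endpoint is at 24 weeks and Protocol 9.5 assumes 10% dropout.

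**Working it through.** **Inputs.** From Protocol 9.5: "Approximately 52 patients diagnosed with RA will be recruited"; "assuming a mean Δ HAQ-DI of -0.21 and a standard deviation of 0.5"; "at two-sided significance level of 0.05 and accounting for a 10% dropout rate". The correlation between baseline DAS28 and HAQ DI change, written ρ for the population and r for the sample, is in neither document. It is assumed over 0 to 0.7.

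**Step 1: the plan's own figure.** The protocol says "The planned sample size provides 80% power for detecting a statistically significant improvement in HAQ-DI". Evaluable n = 52 × 0.9 = 46.8. The noncentrality is (0.21/0.5) × √46.8 = 2.87, and two-sided power from the noncentral t distribution is 80.3%. The stated 80% reproduces. Below, n = 47.

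**Step 2: point estimate.** The model is change = a + b × (DAS28 − sample-mean DAS28) + error. The least-squares solution for a is the sample mean of the change, whatever b is. In one simulated data set (n = 47, DAS28 about 5.5 with SD 1, slope −0.25, all assumed) both came to −0.2875.

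Without centring, the intercept is the mean change − b × mean DAS28, that is, the predicted change at DAS28 = 0. In the same data set it was +0.93. Entry requires DAS28 above 3.2, so this is an extrapolation.

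**Step 3: standard error.**
- Paired t-test: SD/√n = 0.5/√47 = 0.0729.
- ANCOVA, in a given sample: (SD/√n) × √[(1 − r²)(n − 1)/(n − 2)]. This is below the t-test value only if |r| > 1/√(n − 1) = 1/√46 = 0.147. At r = 0 it is 0.0737 (1.1% larger); at 0.3 it is 0.0703 (3.6% smaller); at 0.5, 0.0639 (12% smaller); at 0.7, 0.0527 (28% smaller).
- The true standard error of the mean over repeated samples stays at SD/√n. The ANCOVA version estimates the residual part only, so in population terms it is short by a factor √(1 − ρ²).

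**Step 4: type I error for the population mean change.** With normal data, the sample mean is independent of the residual mean square. Under no true mean change, the ANCOVA statistic is therefore distributed as t with n − 2 = 45 degrees of freedom, divided by √(1 − ρ²). The rejection rate is P(|t45| > 2.014 × √(1 − ρ²)).

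| assumed ρ | √(1 − ρ²) | effective cut-off | rejection rate |
|---|---|---|---|
| 0 | 1.000 | 2.014 | 5.0% |
| 0.2 | 0.980 | 1.973 | 5.5% |
| 0.3 | 0.954 | 1.921 | 6.1% |
| 0.5 | 0.866 | 1.744 | 8.8% |
| 0.7 | 0.714 | 1.438 | 15.7% |

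Simulations at n = 47 agree within about 0.2 percentage points, and the paired t-test stayed at 4.9% to 5.1%. The result hardly depends on n. SAP section 4 gives 100 patients and 13% dropout, so n = 87; the rates at 0.5 and 0.7 are then 8.9% and 15.9%.

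**Step 5: conditional target.** If the quantity of interest is the mean change at the DAS28 values actually sampled, the same ANCOVA test rejects 4.9% to 5.1% of the time at every correlation. The shortfall concerns only the population mean. SAP 5.3 aims to show that treatment improves functioning in subjects with RA, which reads as a population claim.

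**The case against.** **The model is under-specified, and one may be assuming the worst reading.** This is fair. The documents leave the evaluation point and variance open, and the table-shell workbook is not available. But neither natural reading gives a useful check: at the sample mean the estimate is the raw mean, and at zero it lies outside the eligible range. The protocol's ANOVA on severity classes could give a different number if the classes are weighted equally (−0.24 against −0.29 in the simulated data set). That only reweights the same patients, and the SAP has replaced it.

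**The primary result may be the Wilcoxon option.** The SAP history says Wilcoxon was added because normality was violated. If the median is reported, ANCOVA does not repeat the primary estimate. It still only returns the mean that SAP 5.3 already tabulates in Excel Table 3.1.

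**The inflation rests on an unknown correlation.** This stands. It is negligible up to about 0.2 and becomes material from about 0.4 to 0.5. A reader might infer that the ANCOVA always looks at least as significant as the paired test. It does not: when the sample correlation is below 0.147 in absolute value, its standard error is slightly larger.

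**Patients who stop are not ignored.** A reader might infer that the plan is silent on them. It is not: Excel Table 3.2 compares continuing with withdrawn patients. That comparison describes the withdrawn group but gives no estimate for the whole treated cohort.

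**A repeated-measures model assumes missing at random, which SAP 3.5.5 doubts.** This stands and must be stated openly. But carrying the available-case mean over to all treated patients needs a stronger assumption, namely that those without a usable week-24 value changed as much on average as those with one.

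**Conclusion.** The ANCOVA in SAP 2.1, 2.2 and 5.3 cannot serve as a sensitivity analysis for the mean HAQ DI change. That part is algebra and needs no assumed number, only that the adjusted mean is taken at the sample-mean DAS28.

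The second part is conditional. For the population mean change, the usual standard error is too small to the extent that baseline DAS28 predicts change, and the false-positive rate ranges from nominal at zero correlation to about 16% at 0.7. The correlation is assumed throughout, the data are taken as normal, and the problem disappears for inference conditional on the sampled DAS28 values.

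A reader might infer that the primary conclusion itself is compromised. The documents do not support that: the paired t-test holds its level, and no decision rule depends on the ANCOVA. What needs repair is the robustness claim a report could build on it. The change should be made, but it is not critical.

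**What to change.** **Remove the test.** In SAP 2.1, 2.2 and 5.3, stop using ANCOVA to test the mean change, and align Protocol 9.7.4 and 9.7.5. If the model is kept, report only the slope of HAQ DI change on centred baseline DAS28, labelled descriptive, and note that it overlaps with the effect-modification models in Excel Table 11.

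**Add a sensitivity analysis that changes an assumption.** Fit a repeated-measures model of HAQ DI at baseline, week 12 and week 24 in all treated patients with any post-baseline score. State the following:
- Early-termination scores go to the nearest scheduled visit by a written rule. The rule must cover scores before week 6, which lie nearer to baseline than to week 12 (12/2 = 6), and patients who already have a score at the assigned visit.
- The model assumes missing at random. SAP 3.5.5 doubts this, so say so beside the result, and add that the assumption is weaker than the one behind the available-case analysis.
- The target is all treated patients, whereas the primary analysis concerns those continuing, so the two estimates may legitimately differ.

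Keep the continuing-versus-withdrawal comparison as planned.

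**Cost.** SAP wording and one extra model on scheduled data, with no new visits. The gain is limited by what was recorded: Protocol 12.6 provides an early-termination form in only two of its three drop-out situations, and efficacy is not assessed after a patient stops adalimumab (Protocol 9.7.10, SAP 3.5.5).

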* Note: Patient who misses 2 consecutive adalimumab injections or a total of 3 non-consecutive injections within 24 weeks of treatment will be regarded as “the patient not continuing on adalimumab”.

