9.7.6 Additional Secondary Endpoint Analysis

Additional efficacy analysis include:

- Change in HAQ DI score at 24 weeks after the initiation of adalimumab, in those patients continuing on adalimumab, compared with those patients not continuing on adalimumab. The mean changes in these two groups will be compared using an independent t-test.
- Healthcare resource utilization will be described using number and percentage within each category (number of consultations, number of procedures received, number of surgeries, number of hospitalizations and length of stay, number of concomitant medications)
- Associations between disease severity and PROs
- Associations between change in disease severity and change in PROs

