**DOCUMENT HISTORY**

| Version # | Issue Date | Author/Editor | Sections Changed | Change Summary   |
|------------------|-------------------|----------------------|-------------------------|---|
| V0.4             | 30 May, 2019      | [REDACTED]           | Section 2, 5            | 
 
1. Add median (Q1, Q3) for describing continuous variables when normality is violated.
 
2. Use Q1, Q3 to replace 95% Confidence interval of mean, due to the violation of normality.
 
3. Added paired Wilcoxon signed-rank test as an alternative test for paired t-test when normality is violated.
 
  |
| V0.3             | 24 Dec, 2018      | [REDACTED]           | Section 2, 5            | 
 
1. Added paired Wilcoxon signed-rank test as an alternative test for HAQ DI and WPAI analyses, due to the violation of normality.
 
2. Changed ANOVA to ANCOVA for sensitivity analysis of HAQ DI change, because we used continuous DAS28.
 
3. Added Spearman correlation as an alternative method for association analyses, due to the violation of normality.
 
   |
| V0.2             | 2 Jan, 2018       | [REDACTED]           | Section 2, 5            | 
 
1. Patient's impression of change in RA at weeks 12 and 24 after the initiation of adalimumab has been added in the Study Objectives and Statistical Analysis Section according to protocol.
 
2. Disease status of RA (moderate, severe, missing) has been deleted in Table 2, since it's duplicated with DAS28 categorization.
 
3. Dosage of first adalimumab injection has been deleted in Table 2, since the DOSE should be 40MG for all adults.
 
 |
| V0.1             | 8 Aug, 2017       | [REDACTED]           | All                     | Initial Version   |

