## 2.3 Exploratory Objectives

- To describe the change in HAQ DI score at 24 weeks after the initiation of adalimumab, in those patients continuing on adalimumab (as observed population), compared with those patients not continuing on adalimumab (withdrawal population). The mean or median changes in these two groups will be compared using an independent t-test or paired Wilcoxon signed-rank tests.
- Patient's impression of change in RA at weeks 12 and 24 after the initiation of adalimumab, in those patients continuing on adalimumab (as observed population). Each response will be summarized as number and percentage.
- To summarize the healthcare resource utilization using number and percentage within each category (number of consultations, number of procedures received, number of surgeries, number of hospitalizations and length of stay, number and type of concomitant medications)

- To summarize the change in patient satisfaction questions at weeks 12 and 24 after the initiation of adalimumab, in those patients continuing on adalimumab (as observed population). These changes will be summarized as number and percentage of each response and compared with Wilcoxon signed rank test. Satisfaction will also be dichotomized and analyzed over time with Cochran-Armitage test for trends.
- To analyze the associations between disease severity and PROs (HAQ DI, SF-36 domain scales, EQ-5D-3L index, WPAI total lost productivity)
- To analyze the associations between change in disease severity and change in PROs (HAQ DI, SF-36 domain scales, EQ-5D-3L index, WPAI total lost productivity)
- To explore the potential modifying effects of baseline measures on the changes in primary and secondary efficacy outcomes (i.e. PROs). These measures will include age, gender, baseline severity, and other diagnoses/co-morbidities.

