## 5.5 Analysis Plan for Exploratory Objectives

- Excel Table 7 describes the change in 4 patient satisfaction questions at weeks 12 and 24 after the initiation of adalimumab, in those patients continuing on adalimumab (observed population). These changes will be summarized as number and percentage of each response and compared with Wilcoxon signed rank test. Satisfaction will also be dichotomized and analyzed over time with Cochran-Armitage test for trends.
- Excel Table 8 summarizes the patients' global impression of change in RA at weeks 12 and 24 after the initiation of adalimumab, in those patients continuing on adalimumab (as observed population). Each response (very much better, much better, a little better, no change, a little worse, much worse, and very much worse) will be summarized as number and percentage.
- Descriptive statistics will be presented for post-index overall RA related direct healthcare resource utilization (Excel Table 9)
  - Consultations/visits to healthcare professionals for treatment of RA (number of patients with  $\geq 1$  visit; categorized by the treatment department listed in 3.5.4)
  - Procedures received when visiting the healthcare professional(s) for treatment of RA (number of patients with  $\geq 1$  procedure; categories listed in 3.5.4)
  - surgeries received when visiting the healthcare professional(s) for treatment of RA (number of patients with  $\geq 1$  surgery; categories listed in 3.5.4)
  - Hospitalizations in relation to RA (number of patients with  $\geq 1$  admission)
  - Length of stay in days (mean, SD, median)
  - Concomitant medications taken for RA (number of patients with  $\geq 1$  medication; categories listed in 3.5.4))

- Associations between disease severity (measured by DAS28) and PROs (HAQ DI score, SF-36 domain scales, EQ-5D-3L index, WPAI outcomes) will be analyzed using the bivariate linear regression model (Excel Table 10.1). Separate models will be estimated to identify the association between DAS28 and each of the PROs. If normality assumption for the residual of regression is violated, Spearman correlation coefficients and p-values will be estimated instead.

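### The SAP offers a paired signed-rank test to compare continuing with non-continuing patients, who form no pairs; a lesser point is that Cochran-Armitage ignores repeated answers from the same patients

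*SAP*

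**What the plan says.** **Group comparison.** SAP 5.3 says of the HAQ DI change in the observed and withdrawal populations that the "changes in these two groups will be compared using an independent t-test or paired Wilcoxon signed-rank test". SAP 2.3 repeats this: "The mean or median changes in these two groups will be compared using an independent t-test or paired Wilcoxon signed-rank tests". Protocol 9.7.6 (also 9.1 and the abstract) names one test only: "The mean changes in these two groups will be compared using an independent t-test".

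The note at the end of protocol 9.1 defines the groups. A "Patient who misses 2 consecutive adalimumab injections or a total of 3 non-consecutive injections within 24 weeks of treatment" is classed as not continuing, and everyone else is continuing.

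The SAP document history shows how the rank option arrived. V0.3 introduced the paired signed-rank test for the HAQ DI and WPAI analyses because normality was violated. The V0.4 entry reads "Added paired Wilcoxon signed-rank test as an alternative test for paired t-test when normality is violated".

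**Satisfaction.** SAP 5.5 (also 2.3, and protocol 9.1, 9.7.7 and the abstract) states: "Satisfaction will also be dichotomized and analyzed over time with Cochran-Armitage test for trends". Protocol Table 1 has the satisfaction questions answered at baseline, Week 12 and Week 24 by the same patients.

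**The concern.** A signed-rank test needs either one sample of differences or matched pairs. Two mutually exclusive groups provide no pairs, so the test does not exist for this comparison, whatever the group sizes. Neither document mentions a rank-sum test, so nothing elsewhere supplies the right one. The rank option is also a live choice, because the SAP history records that normality failed for HAQ DI.

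An analyst who follows that option could test each group's change against zero and report the two p-values side by side. A reader could then take significance in the large group and none in the small group as evidence that staying on treatment matters. That would be a statement about group size, not about a difference.

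The satisfaction point is smaller. Cochran-Armitage assumes independent samples at each time point. With repeated answers from the same patients its variance is wrong, and the question is in which direction and by how much.

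**Working it through.** **The plan's own figure.** Protocol 9.5 assumes a mean change of -0.21 and SD 0.5, "at two-sided significance level of 0.05 and accounting for a 10% dropout rate", with 80% power. Normal approximation: (0.5 × (1.960 + 0.842) / 0.21)² = 44.5, so 45 completers; 45/0.9 = 50. With the exact t distribution 47 completers are needed (power 80.5%); 47/0.9 = 52.2, so 53, while 47 × 1.1 = 51.7, so 52. The planned 52 is reproduced to within 2. It concerns the primary paired test, which this point does not touch. The documents give no size or power for the group comparison or for the satisfaction trend.

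**(a) Group comparison**

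Inputs: total 52, mean change -0.21 and SD 0.5 (protocol 9.5). Group sizes are an assumption, with dropout standing in for non-continuation: 47 v 5 (the protocol's 10%), 45 v 7 (13%, the rate in SAP section 4, applied to 52) and 42 v 10. Change scores are taken as normal, and non-continuing patients are assumed to have one.

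The smallest exact two-sided signed-rank p-value with m observations is 2/2^m. For m = 5 it is 2/32 = 0.0625, so five patients can never reach 0.05.

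Suppose there is no true group difference and each group is tested separately against zero. If a and b are the chances of significance in the two groups, the chance that they disagree is a(1−b) + b(1−a). The rank-sum test is shown for comparison, with power for a true change of -0.21 v 0.

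| Continuing v not | a | b | Disagree | Rank-sum size | Rank-sum power | t-test power |
|---|---|---|---|---|---|---|
| 47 v 5 | 78% | 0% | 78% | 4.4% | 13% | 14% |
| 45 v 7 | 77% | 14% | 70% | 4.8% | 17% | 18% |
| 42 v 10 | 73% | 22% | 63% | 4.7% | 20% | 21% |

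These are simulations (4,000 runs for signed-rank, 6,000 for rank-sum). Repeat runs moved the disagreement figures by at most four percentage points.

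Forcing the test through by pairing patients arbitrarily does no better, because it uses only as many patients as the smaller group. For an assumed group difference of 0.5 with SD 0.5, power is 0% for arbitrary pairs, 51% for rank-sum and 55% for the t-test at 47 v 5. At 42 v 10 it is 49%, 77% and 79%.

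**(b) Satisfaction trend**

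With scores 0, 1, 2 for the three visits, the trend statistic is the number satisfied at Week 24 minus the number satisfied at baseline. Under no trend, Cochran-Armitage gives it variance 2np(1−p). With within-patient correlation ρ the true variance is 2np(1−p)(1−ρ). The true size at nominal 5% is therefore 2 × (1 − Φ(1.96/√(1−ρ))). For ρ = 0.3, 1.96/√0.7 = 2.34, which gives 1.9%.

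The documents give no correlation or response rates, so the values below are assumed, with n = 47 (20,000 simulated trials for power).

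| ρ | Cochran-Armitage size | Power at 40/50/60%: within-patient contrast | Power at 30/45/60%: Cochran-Armitage v contrast |
|---|---|---|---|
| 0 | 5.0% | 50% | 84% v 85% |
| 0.1 | 3.9% | 54% | 86% v 88% |
| 0.3 | 1.9% | 63% | 88% v 95% |
| 0.5 | 0.6% | 78% | 93% v over 99% |

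At 40/50/60%, Cochran-Armitage power stays at 48% to 50% throughout. The size of the contrast test was 4.6% to 5.6%.

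**The case against.** The wording error in (a) is hard to dispute. The case on the other side concerns how much it matters.

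- The comparison is exploratory in SAP 2.3 and additional secondary in the protocol. A valid test is named first, and the slip would probably surface at programming. This limits the urgency. It does not make the prescribed rank option usable.
- No text plans separate tests per group, so the disagreement rates describe a misuse rather than the plan. That is fair: they illustrate what could happen and are not a forecast.
- The rank option exists because normality failed, yet the simulation assumes normality. In an illustrative skewed case with the same mean and SD, disagreement falls to about 51% to 56% and rank-sum power rises to about 27% to 44%. The normal-based power of 13% to 20% is therefore not a general figure.
- The non-continuing group could be much larger, since SAP 1.1 puts average use in China at three months. At 26 v 26 under normality, disagreement is about 50% and rank-sum power about 30%.
- The SAP refers to a table shell that is not available here and may list a different test. The V0.3 history entry is also broad enough to cover this comparison, so carry-over from the paired analyses is a plausible explanation, not a proven one.
- Protocol 9.7.10 and SAP 3.5.5 say efficacy is not assessed after discontinuation, while Table 1 schedules the HAQ at early termination. The SAP does not say which value serves as Week 24 for non-continuing patients. That gap stands and is not closed by changing the test.
- Part (b) errs towards missing a trend, uses questions the SAP calls unvalidated, and sits beside a signed-rank test that does respect pairing. All true, which is why it is minor.

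**Conclusion.** The concern holds. For (a), the SAP's non-parametric option cannot test the difference between continuing and non-continuing patients. This follows from the group definition alone and needs no assumption. It should be fixed, because the plan prescribes a test that cannot answer its stated question.

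The illustrative size, 63% to 78% disagreement with no true difference, rests on normal change scores, dropout as a stand-in for non-continuation, and an analyst falling back on separate tests. With skewed scores it is nearer one half. The rank-sum test is valid, but it does not make so unbalanced a comparison conclusive.

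For (b), Cochran-Armitage is conservative when answers within a patient are positively correlated. It loses power and does not create false positives. The loss is close to nil near zero correlation and substantial at 0.3 to 0.5, but the documents give no correlation, so confidence in its size is moderate.

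The primary paired analysis and the planned 52 patients are unaffected by either point.

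**What to change.** **(a)** In SAP 2.3 and 5.3, for the observed-versus-withdrawal comparison only, replace the paired Wilcoxon signed-rank test with the Wilcoxon rank-sum (Mann-Whitney) test. The signed-rank test stays as the alternative to the paired t-test for within-patient changes. This costs a few words in two sections. The table shell for Excel Table 3.2 should be checked for the same wording.

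**(b)** In SAP 2.3 and 5.5, replace Cochran-Armitage with a test on the within-patient linear contrast of satisfied yes/no; for equally spaced visits this is Week 24 minus baseline. Record it as a departure from protocol 9.1, 9.7.7 and the abstract, which also name Cochran-Armitage. This costs one sentence in two sections and a note of the departure.

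Both changes use standard SAS procedures and need no new data.
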